#### 4.4.8 Participant-reported local tolerability at the injection site and systemic complaints (eDiary app)

All participant-reported reactions at injection site and systemic complaints will be listed and number and percentage of subjects with presence of symptoms and symptom severity, if applicable (refer to code lists in Section 2.2), in each treatment group will be summarized in frequency tables.

#### 4.4.9 Inflammatory markers

At each scheduled visit absolute values and change from baseline of the inflammatory markers will be summarized by using descriptive statistics of n, mean, SD, SEM, median, Min, and Max for each treatment group and overall.

#### 4.5 Analysis of efficacy endpoints

All observed and change from baseline efficacy endpoints will be listed by treatment group, subject and visit. Individual graphs by visit will also be generated.

All observed and change from baseline efficacy endpoints with multiple post-baseline measurements (including but not limited to levels of anti-aSyn, anti-UBITH and anti-CpG1 antibody titers in serum and their antibody parameters of  $C_{max}$ ,  $t_{max}$ ,  $AUC_{last}$  and  $t_{1/2}$ , which are derived by non-compartmental analysis and total and free aSyn concentrations in blood) will be summarized using descriptive statistics of n, mean, SD, SEM, median, Min and Max by treatment group, visit (and time when applicable), and will also be presented graphically as mean over time, with standard deviation as error bars.

All observed and change from baseline efficacy endpoints with single post-baseline measurement (including but not limited to levels of anti-aSyn, anti-UBITH and anti-CpG1 antibody titers in CSF and their antibody parameters of  $C_{max}$ ,  $t_{max}$ ,  $AUC_{last}$  and  $t_{1/2}$ , which are derived by non-compartmental analysis and total and free aSyn concentrations in CSF, T-cell ELISpot specific for the immunizing peptide as well as MDS-UPDRS Parts II and III sub scores and total scores) will be summarized using descriptive statistics of n, mean, SD, SEM, median, Min and Max by treatment group, and will also be presented graphically as mean in a bar graph, with standard deviation as error bars.

To establish whether significant treatment effects can be detected on the observed efficacy endpoints with multiple post-baseline measurements, such as serum levels of anti-aSyn, anti-UBITH and anti-CpG1 antibody titers in blood, each parameter will be analysed with a mixed model analysis of covariance (ANCOVA) with treatment, time and treatment by time as fixed factors and subject as random factor and the (average) baseline measurement as covariate.

The efficacy endpoints of levels of anti-aSyn, anti-UBITH and anti-CpG1 antibody titers in serum and in CSF will initially be analysed without transformation, but if the data suggest otherwise, log-transformation may be applied. Log-transformed parameters will be back-transformed after analysis where the results may be interpreted as percentage change. Residual Q-Q plots are produced to check the assumption of normality of the error term in the mixed effects models as described above. This is done by visual inspection and the Shapiro-Wilk test statistic.

The observed efficacy endpoints with single post-baseline measurement, such as levels of anti-aSyn, anti-UBITH and anti-CpG1 antibody titers in CSF, will be analysed with a mixed model analysis of variance (ANOVA) with treatment as fixed factors and subject as random factor and the (average) baseline measurement as covariate.

The Kenward-Roger approximation will be used to estimate denominator degrees of freedom and model parameters will be estimated using the restricted maximum likelihood method.

The general treatment effect and specific contrasts will be reported with the estimated difference and the 95% confidence interval, the least square mean estimates and the p-value. Graphs of the Least Squares Means (LSM) estimates over time by treatment group will be presented with 95% confidence intervals as error bars, as well as change from baseline LSM estimates.

The following contrasts will be calculated within the model using observed data:

- Treatment with 3 vaccinations of 40 $\mu$ g UB-312 versus pooled Placebo
- Treatment with 3 vaccinations of 100  $\mu$ g UB-312 versus pooled Placebo
- Treatment with 1 vaccination of 40  $\mu$ g, followed by 2 vaccinations of 300  $\mu$ g UB-312 versus pooled Placebo
- Treatment with 3 vaccinations of 300  $\mu$ g UB-312 versus pooled Placebo
- Treatment with 1 vaccination of 40  $\mu$ g, followed by 2 vaccinations of 1000  $\mu$ g UB-312 versus pooled Placebo
- Treatment with 3 vaccinations of 1000  $\mu$ g UB-312 versus pooled Placebo
- Treatment with 3 vaccinations of 2000  $\mu$ g UB-312 versus pooled Placebo

Notes:

- (1) Change from baseline values calculated at subject level for each efficacy endpoint will only be used for descriptive purposes.
- (2) Above contrast will be adjusted to obtain for change from baseline endpoints.
- (3) The treatment groups across the cohorts will also be compared pairwise.

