## 1.9 Sample size determination and total expected number of participants

The early phase clinical trial is exploratory in nature to assess the primary objectives of safety, tolerability, and immunogenicity of UB-312. Power calculations for comparison of adverse experience rates are too imprecise to be clinically meaningful because the actual rates are not even approximately known. The objective of evaluating the immunogenicity of UB-312 on anti-aSyn antibodies in cerebrospinal fluid will be an estimation, not a comparison. So, no power calculation is required.

Approximately 50 healthy participants (8 participants in the lowest dose cohort and 7 participants per cohort for ascending cohorts) and approximately 20 participants with PD will be enrolled to receive UB-312 treatment or matching placebo.

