### **1.11.3 End of Treatment Analysis in Part B**

The analysis of the end of treatment for Part B will be performed when the last patients in Part B complete the EOT/ET visit for administrative purposes. An external statistical vendor is planned to performance the analyses and in house study team remains blinded. The study team will remain blinded to the treatment of individual patients until the end of the study.

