## 2 STUDY ENDPOINTS

### 2.1 Demographics and Baseline Characteristics

The baseline value is defined as the last available value before the first injection of study drug. The following demographic and baseline disease characteristics will be collected.

Demographic characteristics are age (unit: years), gender (levels: male or female), height (unit: cm), body weight (unit: kg), Body Mass Index (BMI, unit: kg/m^2) and race (levels: White/Black or African American/Asian/American Indian or Alaska Native/Native Hawaiian or other Pacific Islander/Mixed/Other).

Disease characteristics are only applicable for Part B and defined as disease duration (unit: years), Hoehn and Yahr (H&Y) stage (unit: none) at screening and baseline scores of Unified Parkinson's Disease Rating Scale (unit: none).

Complete physical and neurological examination will be performed at screening and brief physical and neurological examination (changes in specific findings) will be performed during post-baseline visits.

Abnormalities in physical examinations will be collected for:

- abdomen (levels: Yes or No);
- breast (levels: Not Done, Yes, or No);
- central nervous system (levels: Yes or No);
- ear, nose, throat (levels: Yes or No);
- extremities (levels: Yes or No);
- eyes (levels: Yes or No);
- head neck (levels: Yes or No);
- heart (levels: Yes or No);
- lungs/thorax (levels: Yes or No);
- lymph nodes (levels: Yes or No);
- musculo-skeletal system (levels: Yes or No);
- psychiatric examination (levels: Yes or No);
- skin (levels: Yes or No);
- other body systems (levels: Yes or No).

Abnormalities in neurological examinations will be collected for:

- Abnormality in Romberg test (levels: Yes or No);
- Abnormality in Pupillary reaction to light (levels: Yes or No);
- Abnormality in ocular movement and vision fields (levels: Yes or No);
- Abnormality in finger-nose test with eyes closed (levels: Yes or No);
- Abnormality in Heel-to-shin test (levels: Yes or No);
- Abnormality in Dysdiadochokinesis: Subject to quickly put fingertips of finger II-IV one after the other on the tip of thumb (levels: Yes or No);
- Abnormality in Tandem-Walk: Stepping on a line on the floor with eyes open (levels: Yes or No);
- Abnormality in elbow and knee flexor or extensor strength or grip strength
- Abnormality in muscle stretch reflexes (levels: Yes or No);
- Abnormality in soft touch with cotton wool on all four extremities (levels: Yes or No);

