## 2.3 Efficacy endpoints

Blood and CSF-based antibody variables are collected during baseline and post-baseline visits. Immunogenicity (level,  $C_{max}$ ,  $t_{max}$ ,  $AUC_{0-last}$ , half-life) will be based on the observed data:

- anti-aSyn antibody titers in serum and CSF
- anti-UBITH antibody titers in serum and CSF
- anti-CpG1 antibody titers in serum and CSF

The following antibody parameters will be derived by non-compartmental analysis of the serum anti-aSyn, and may be derived also for anti-UBITH and anti-CpG1 antibody titers - time profiles following the third study drug injection:

- $C_{max}$ : Maximum titer level
- $t_{max}$ : Time of maximum titer level (days after last injection)
- $AUC_{0-last}$ : Area under the titer – time curve from time of last injection to time of last measurable level.
- $t_{1/2}$ : Half-life (1/day)

Serum and CSF levels of antibodies targeting the carrier (UBITH1), CpG1, and different aSyn forms such as monomers, oligomers and fibrils may be measured during the study, and will be based on the observed and change from baseline data.

Free and total aSyn values will be measured during the study and will be based on the observed and change from baseline data.

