### 3.2 Handling of missing data

All missing or incomplete safety and efficacy data, including dates and times, are treated as such. Missing test results or assessments will not be imputed. Missing safety and efficacy data, indicated as 'M' in the data listing, will be assumed to be missing-at-random (MAR) when the statistical mixed model using SAS PROC MIXED is employed.

For graphical and summary purposes efficacy and safety values below the limit of quantification (LOQ; if applicable) will be set to half ( $\frac{1}{2}$ ) of the LOQ. For analysis no undetermined values will be replaced, except pre-values below the LOD/LOQ that are used as covariate. They will be replaced by 50% of the LOD/LOQ.

For calculation of  $AUC_{last}$ , all titer levels below the LOQ will be set to half ( $\frac{1}{2}$ ) of the LOQ. For calculation of half-life all levels below the LOQ will be treated as "missing".

If data points for antibody titers are missing, the AUC parameters will be derived by interpolating with regard to the two neighbouring non-missing values.

If the actual sampling time is missing, but a valid antibody value is measured, the scheduled protocol time will be used for the calculation of the antibody parameters.

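### SAP 3.2 leaves post-dose titres below LOQ unreplaced and does not say how they enter the titre models; a lesser gap is that the switch from raw to log scale has no trigger

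*SAP*

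**What the plan says.** The protocol synopsis makes change from baseline in blood and CSF anti-aSyn titres a primary outcome measure. The SAP models these titres under its efficacy heading.

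**Values below LOQ (SAP 3.2).** The treatment differs by use:
- Summaries and graphs: half LOQ.
- AUClast: half LOQ.
- Half-life: treated as missing, expressly.
- Baseline titre as covariate: 50% of LOD/LOQ.
- Post-dose titre as model outcome: "For analysis no undetermined values will be replaced, except pre-values below the LOD/LOQ that are used as covariate".

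The same section says that missing data "will be assumed to be missing-at-random (MAR) when the statistical mixed model using SAS PROC MIXED is employed".

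**Scale (SAP 4.5).** Serum and CSF titres "will initially be analysed without transformation, but if the data suggest otherwise, log-transformation may be applied". Q-Q plots and Shapiro-Wilk are planned for the residuals. Log results are to be back-transformed and read as a percentage change; otherwise an estimated difference with 95% CI is reported.

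**CSF.** SAP 4.5 gives a one-value model to "The observed efficacy endpoints with single post-baseline measurement, such as levels of anti-aSyn, anti-UBITH and anti-CpG1 antibody titers in CSF". SAP 1.9 adds: "The objective of evaluating the immunogenicity of UB-312 on anti-aSyn antibodies in cerebrospinal fluid will be an estimation, not a comparison".

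**The concern.** A result reported only as below LOQ has no number. SAP 3.2 says it is not replaced but stops there. PROC MIXED omits a record whose outcome has no value, so the likely practical result is that the lowest titres leave the analysis. They leave because of their own size, so the missing-at-random assumption does not cover them.

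The loss would fall mainly on placebo, where low titres are expected. A placebo participant who stays below LOQ throughout would have a baseline of half LOQ and no outcome at all, and would drop out of the model. The descriptive tables, which use half LOQ, and the model estimates would then rest on different data for the same endpoint.

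The scale question is separate. Without a cut-off, or a statement of which result leads, the reported effect may be a difference or a percentage change, and that is settled only once the data are seen.

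**Working it through.** The plan states no titre effect, SD, LOQ or power, so there is no figure to reproduce. Everything below is illustrative.

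**1. Group sizes (protocol synopsis, SAP 1.10).** Pooled placebo is 2 + 6 × 1 = 8 in Part A and 2 × 3 = 6 in Part B. Active arms have 6 and 7.

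**2. Log scale, one visit.** Assume log10 titres are normal with SD σ, placebo mean 0 and active mean δ = log10 5 = 0.699. Put the LOQ at the placebo percentile p, so ℓ = σ·z_p, and let a = (ℓ − δ)/σ.
- Mean of quantified values: placebo σφ(z_p)/(1 − p); active δ + σφ(a)/(1 − Φ(a)).
- Dropped: the contrast is the difference of these two means.
- Half LOQ: each arm mean is (share below) × (ℓ − 0.301) + (share above) × (quantified mean).

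With σ = 0.5:

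| Placebo below LOQ | 25% | 50% | 75% |
|---|---|---|---|
| ℓ | −0.337 | 0 | 0.337 |
| Active below LOQ | 1.9% | 8.1% | 23.5% |
| Quantified mean, placebo | 0.212 | 0.399 | 0.636 |
| Quantified mean, active | 0.723 | 0.781 | 0.900 |
| Dropped: log10 difference | 0.511 | 0.382 | 0.264 |
| **Dropped: fold** | **3.2** | **2.4** | **1.8** |
| Half LOQ: mean, placebo | −0.001 | 0.049 | 0.186 |
| Half LOQ: mean, active | 0.697 | 0.693 | 0.697 |
| **Half LOQ: fold** | **5.0** | **4.4** | **3.2** |

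Simulation gave 3.2/2.4/1.8 dropped and 5.0/4.4/3.1 at half LOQ. A censored-likelihood fit (one visit, Part A) gave 4.9/4.9/4.3.

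**3. Range over SD.** The same formulas give, for σ = 0.3, dropped 3.7/2.9/2.2 and half LOQ 5.4/5.3/4.7. For σ = 0.7 they give dropped 3.0/2.2/1.7 and half LOQ 4.7/3.8/2.6.

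**4. Repeated visits.** A simulated random-intercept model with four visits (within-subject correlation 0.6, σ = 0.5) gave 3.5/2.5/1.9 dropped in Part A and 3.5/2.5/1.8 in Part B. Borrowing across visits recovers little.

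**5. Raw scale.** With s = σ·ln 10, m = ln of the arm's geometric mean and l = ln LOQ, the mean of quantified values is exp(m + s²/2)·Φ((m + s² − l)/s)/Φ((m − l)/s). For σ = 0.5 and p = 50%, s = 1.151 and exp(s²/2) = 1.940.
- True difference: 4 × 1.940 = 7.76.
- Dropped: placebo 1.940 × 0.875/0.5 = 3.40; active 9.70 × 0.995/0.919 = 10.50; difference 7.10, or 8.5% smaller.
- At p = 25% and 75% the loss is 5% and 10%.
- At σ = 0.7 and p = 75% the difference is instead about 11% larger, so on the raw scale the direction is not assured.

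**6. Placebo left at a visit.** If values are dropped, the chance that none remains is p^n. At 75% below LOQ this is 0.75^8 = 10.0% in Part A and 0.75^6 = 17.8% in Part B.

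**7. Scale check, serum.** With four post-dose visits and σ of 0.3 to 0.7, Shapiro-Wilk at 5% rejected raw residuals in 100% of simulated Part A trials and 98.9 to 100% of Part B trials.

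**8. Scale check, CSF in Part B.** SAP 4.5 treats CSF as having one post-baseline value. Protocol Table 1 and SAP Appendix 1 collect CSF at V1, at EOT/ET and at the last follow-up, which is two planned post-baseline samples. Share of simulated trials left raw, for σ = 0.3/0.5/0.7:

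| Assumed rises | One visit | Two visits |
|---|---|---|
| 5 and 20 | 22/14/7% | 3/1/0% |
| both 10 | 41/17/7% | 12/2/0% |
| 2 and 4 | 43/18/7% | 16/3/0% |

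If Parts A and B share one single-visit model, raw was kept in 0 to 2.5%. SAP 3.6 pools placebo across cohorts, and SAP 4.5 does not say whether the parts are modelled separately.

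**The case against.** SAP 3.2 does contain a rule, so a reader who infers that values below LOQ have none goes too far. Non-replacement is stated, and AUClast, half-life and the baseline covariate each have their own handling. What stands is narrower: for the post-dose outcome, the rule ends before saying what the model receives. Dropping is one reading. SAP 3.2 uses the word missing only for half-life, and the laboratory's own number, if reported, might be kept. Every dropped figure above rests on the first reading.

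A reader might also infer that no scale is named, or that a raw serum analysis would lose most true effects. SAP 4.5 does name raw as the starting scale, with diagnostics. A severe loss in serum requires the analyst to ignore a check that would almost always point to logs.

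Nor do the documents show that the scale would be chosen after unblinding. The blind data review in SAP 3.3 is not given this decision, but nothing excludes a blinded choice.

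Two limits remain. Log-normal data favour the log model by construction, and Shapiro-Wilk at 5% is not the SAP's full check, which includes visual inspection. The study is also exploratory, without a formal hypothesis (SAP 4.5.1). That lowers the stakes but does not settle which estimate is reported for a primary outcome.

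**Conclusion.** The point holds in its limited form and should be fixed. The main defect is the unfinished rule for post-dose titres below LOQ. If they are omitted, missing at random does not fit, and a true 5-fold rise reads as 1.7- to 3.7-fold on the log scale across the settings shown. The raw-scale effect is small at SD 0.5 and may reverse at SD 0.7. These sizes rest on assumed log-normal titres, an assumed LOQ and the dropped reading; they show direction, not a forecast.

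The scale gap is secondary. For serum, little is lost if the check is followed. For CSF, the risk of staying raw ranges from near nil to about 43% in Part B, depending on SD, rise, one or two modelled samples, and joint or separate models by part. The CSF sample count in SAP 4.5 and in the schedules must be reconciled.

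**What to change.** Make these changes before any treatment-coded titre analysis. That includes the Part B end-of-treatment analysis, for which SAP 1.11.3 says: "An external statistical vendor is planned to performance the analyses and in house study team remains blinded".

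- **SAP 4.5.** Make log10 titre the main analysis for serum and CSF, with log10 baseline as covariate; SAP 2.1 already fixes baseline: "The baseline value is defined as the last available value before the first injection of study drug". Report geometric mean ratios with 95% CI. Keep the raw scale as supportive, and use residual checks as diagnostics that do not change the main scale. State how many post-baseline CSF values are modelled and whether Parts A and B are fitted separately.
- **SAP 3.2.** Enter post-dose titres below LOQ in the titre models at half LOQ. Add a left-censored sensitivity analysis on the log10 scale wherever it can be fitted. Show the number below LOQ by arm and visit.

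The cost is SAP wording, table shells and one extra program. Effects will read as ratios. Half LOQ can err either way: for a true 5-fold rise it gives 5.4 at SD 0.3 with 25% of placebo below LOQ, and 2.6 at SD 0.7 with 75%. That is the reason for the censored analysis. Where no placebo value is quantifiable, the censored model cannot be fitted, and only the half-LOQ result and the counts can be shown.

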1.1 Study Schematic

Figure 1 Study Design Schematic

[figure not shown]

Table 1 **Study Schedule of Assessments**

Visit	Screening	V1* Vaccination 1	V2	V3 Vaccination 2	V4	V5	V6 Vaccination 3	V7	V8	EOT or ET	Unscheduled Visit ¹⁵	Follow-Up
Week	Up to 6 weeks	1	2	5	6	9	13	14	17	21	N/A	29, 37, 45
Day*	-42 ~ 0	1¹⁴	8 (± 1)	29¹⁴ (± 3)	36 (± 3)	57 (± 3)	85¹⁴ (± 3)	92 (± 3)	113 (± 3)	141 (± 7)	N/A	197, 253, 309 (± 7)
Free and total aSyn ¹		X	X	X	X	X	X	X	X	X	X	X
ELISpot ¹		X							X	X ¹⁹		
HLA typing ¹		X										
Blood collection for future research ^{1,11}		X	X	X	X	X	X	X	X	X		
CSF collection ^{1,21}		X								X	X	X ¹⁸
Study Drug IM Injection		X		X			X					
Injection Site Reaction review ^{1,3}		X ¹⁴	X	X ¹⁴	X		X ¹⁴	X			X	
For Part B only												
Hoehn and Yahr	X											
MDS-UPDRS (Parts II to III ^{1,12})		X								X	X	X ¹⁸
DaTscan	X ^{8,13}											
MoCA		X								X		X ¹⁸

AE=adverse event; CSF=cerebrospinal fluid; ECG=electrocardiogram; EOT = End of Treatment; ET = Early Termination; HBV = Hepatitis B virus; HCV=hepatitis C virus; HIV = human immunodeficiency virus; IM=intra-muscular; MDS-UPDRS=Movement Disorders Society – Unified Parkinson’s Disease Rating Scale; MoCA = Montreal Cognitive Assessment; MRI=magnetic resonance imaging; SAE=serious adverse event

* Time points for all visits are relative to Day 1 (day of first IMP administration). Every effort should be made to schedule visits as close as possible to the time point specified in the Schedule of Assessments. If a visit cannot be scheduled within the specified window, the timing of the visit and procedures should be discussed with the Sponsor.

1. Prior to administration of study IP at each applicable visit. Screening and V1 visits can be rescheduled if measured for moderate or severe illness and/or fever $>38.0^{\circ}$ Celsius within 1 week prior to visit.
2. AEs/SAEs recorded from time of informed consent up to and including Follow-up.
3. Also performed 45 minutes (+/- 15 minutes) and approximately 6 hours after administration of study IP at each applicable visit.
4. Including height (screening only); no need to repeat weight measurement for post-injection vital signs.
5. Full neurological exam at screening and last FU visit, brief neurological examination at other visits.
6. ECG in triplicate.

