### For Part B Outcome Measures

MDS-UPDRS Parts II and III are rated at baseline, EOT/ET, and the last follow up visits. MDS-UPDRS Parts II and III sub scores and total scores will be based on the observed and change from baseline data.

MDS-UPDRS part II questionnaire consists of the following items:

- UPDRS part 2 Speech (MDS\_201; Numeric: 0, 1, 2, 3, 4; Levels: Normal or Slight or Mild or Moderate or Severe)
- UPDRS part 2 Saliva and drooling (MDS\_202; Numeric: 0, 1, 2, 3, 4; Levels: Normal or Slight or Mild or Moderate or Severe)
- UPDRS part 2 Chewing and swallowing (MDS\_203; Numeric: 0, 1, 2, 3, 4; Levels: Normal or Slight or Mild or Moderate or Severe)
- UPDRS part 2 Eating tasks (MDS\_204; Numeric: 0, 1, 2, 3, 4; Levels: Normal or Slight or Mild or Moderate or Severe)
- UPDRS part 2 Dressing (MDS\_205; Numeric: 0, 1, 2, 3, 4; Levels: Normal or Slight or Mild or Moderate or Severe)
- UPDRS part 2 Hygiene (MDS\_206; Numeric: 0, 1, 2, 3, 4; Levels: Normal or Slight or Mild or Moderate or Severe)
- UPDRS part 2 Handwriting (MDS\_207; Numeric: 0, 1, 2, 3, 4; Levels: Normal or Slight or Mild or Moderate or Severe)
- UPDRS part 2 Doing hobbies and other activities (MDS\_208; Numeric: 0, 1, 2, 3, 4; Levels: Normal or Slight or Mild or Moderate or Severe)
- UPDRS part 2 Turning in bed (MDS\_209; Numeric: 0, 1, 2, 3, 4; Levels: Normal or Slight or Mild or Moderate or Severe)

- UPDRS part 2 Tremor (MDS\_210; Numeric: 0, 1, 2, 3, 4; Levels: Normal or Slight or Mild or Moderate or Severe)
- UPDRS part 2 Getting out of bed, a car or a deep chair (MDS\_211; Numeric: 0, 1, 2, 3, 4; Levels: Normal or Slight or Mild or Moderate or Severe)
- UPDRS part 2 Walking and balance (MDS\_212; Numeric: 0, 1, 2, 3, 4; Levels: Normal or Slight or Mild or Moderate or Severe)
- UPDRS part 2 Freezing (MDS\_213; Numeric: 0, 1, 2, 3, 4; Levels: Normal or Slight or Mild or Moderate or Severe)

MDS-UPDRS part III questionnaire consists of the following items:

- MDS-UPDRS 3a Medication use for patient's clinical state (MDS\_3a; Numeric: 0, 1; Levels: No or Yes)
- MDS-UPDRS 3b Patient's clinical state on medication (MDS\_3b; Numeric: 0, 1, 2; Levels: ON or OFF or N/A. No medication)
- MDS-UPDRS 3c On levodopa (MDS\_3c; Numeric: 0, 1; Levels: No or Yes)
- UPDRS part 3 Speech (MDS\_301; Numeric: 0, 1, 2, 3, 4; Levels: Normal or Slight or Mild or Moderate or Severe)

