##### 3.1.4 Antibody Parameters

Values of the maximal concentration ( $C_{\max}$ ) and the time to reach  $C_{\max}$  ( $t_{\max}$ ) are obtained directly from the individual anti-aSyn, anti-UBITH and anti-CpG1 antibody titer-time profiles. If the same maximum titer levels are observed at two or more time points, the earliest time point should be used as  $t_{\max}$ .

For each individual antibody titer-time profiles the area under the curve from 0 to the last quantifiable observation ( $AUC_{0\text{-last}}$ ) and the half-life will be calculated. The  $AUC_{0\text{-last}}$  will be calculated using the linear trapezoidal rule. The half-life will be calculated as  $t_{1/2}=\ln(2)/\lambda_z$ , where  $\lambda_z$  is the terminal elimination rate constant determined by unweighted least squares regression of the terminal part of each individual log/linear concentration-time profile. The following rules will be applied to determine the terminal elimination phase:

- The slope of the regression line must be negative ( $\lambda_z > 0$ ).
- Sample at  $t_{\max}$  cannot be included.
- At least 3 data points should be used.
- $R^2 > 0.85$

In general, the more data points that are used in the estimation, the better. The number of data points will be selected automatically to achieve the largest adjusted  $R^2$  value. If two adjusted  $R^2$  values (based on different number of data points) deviated with less than 0.0001, then the fit based on the most data points will be selected.

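### SAP 4.5 treats CSF antibody titres and MDS-UPDRS II/III as measured once after baseline, but two measurements are scheduled (Weeks 21 and 45) and the analysed visit is not named

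*SAP*

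**What the plan says.** SAP 4.5 defines two classes of efficacy endpoint.

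- **Multiple post-baseline measurements.** These are summarised by treatment group and visit, plotted over time, and modelled with treatment, time and their interaction.
- **Single post-baseline measurement.** The paragraph opening "All observed and change from baseline efficacy endpoints with single post-baseline measurement" gives these a summary by treatment group only, shown as a bar graph. It lists CSF antibody titres, CSF total and free aSyn, and "T-cell ELISpot specific for the immunizing peptide as well as MDS-UPDRS Parts II and III sub scores and total scores". The model sentence reads "The observed efficacy endpoints with single post-baseline measurement, such as levels of anti-aSyn, anti-UBITH and anti-CpG1 antibody titers in CSF, will be analysed", and what follows is treatment as the fixed factor, subject as random and baseline as covariate.

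The same summary paragraph asks for non-compartmental parameters in CSF: "anti-CpG1 antibody titers in CSF and their antibody parameters of" Cmax, tmax, AUC and half-life.

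Other sections differ. Protocol Table 1 and SAP Appendix 1 mark CSF collection and MDS-UPDRS at V1, at EOT/ET (Week 21) and, through footnote 18, at the last follow-up visit (Week 45). SAP 2.3 says the same in words: "MDS-UPDRS Parts II and III are rated at baseline, EOT/ET, and the last follow up visits". MoCA has the same visits, and SAP 2.3 summarises it at end of treatment and at follow-up.

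**The concern.** The class decides the analysis. Only the multiple-measurement class receives by-visit group summaries and a treatment-by-time model, so endpoints placed in the wrong class lose both.

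This matters most for CSF anti-aSyn titre. The protocol synopsis makes it part of a primary outcome, and SAP 1.9 describes the CSF objective as estimation. An estimate needs a stated time. Week 21 and Week 45 ask different questions: response near the end of treatment, and persistence long after the last dose. As written, a reader of the report could not tell whether a CSF result refers to Week 21, Week 45 or a mixture. MDS-UPDRS and CSF aSyn concentrations have the same problem but are exploratory outcomes.

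**Working it through.** **Step 1. Count the scheduled measurements.** SAP 4.5 implies 1. Both schedules give 2: EOT/ET (Week 21, Day 141) and last follow-up (Week 45, Day 309). The SAP's count does not reproduce. For CSF total and free aSyn the count follows from the CSF collection row, since no separate row exists. ELISpot is taken at V8, or at EOT if V8 was missed, so it does fit the single class.

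**Step 2. How far apart are the visits?** The third dose is scheduled on Day 85.
- Week 21: 141 − 85 = 56 days after it.
- Week 45: 309 − 85 = 224 days after it.
- Gap: 309 − 141 = 168 days.

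**Step 3. Does the code settle which visit is used?** The single-measured code in SAP Appendix 2 contains `occasion`, defined there as period, and omits `expdelta`, defined there as time. It has no interaction with treatment. Two readings remain.

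*One row per subject.* Nothing is averaged, but the visit is unnamed. The covariance is (σ²_subject + σ²_residual)·I, so the random subject term cannot be separated from the residual. In a numerical check the REML log-likelihood was −7.11875 for all four splits of the variance tried.

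*Two rows per subject.* Let the treatment effect be 1 at Week 21 and f at Week 45 (f is assumed; the documents give no value). With complete data the treatment coefficient equals the contrast of subject means:

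estimate = (1 + f)/2

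| f | Estimate, as a multiple of the Week 21 effect |
|---|---|
| 0 | 0.500 |
| 0.25 | 0.625 |
| 0.5 | 0.750 |
| 0.75 | 0.875 |
| 1 | 1.000 |

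The expected coefficient takes these values in both designs:
- Part A: 7 active groups × 6, plus 2 + 6 × 1 = 8 placebo, gives 50 participants and 100 rows.
- Part B: 7 + 7 active, plus 3 + 3 = 6 placebo, gives 20 participants and 40 rows.

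The results are the same with or without baseline, with or without a visit main effect, and at within-subject correlations of 0, 0.3, 0.5 and 0.8. The same f was assumed in every active arm. A simulation with 7 active and 6 placebo participants gave averages of 0.507, 0.626, 0.754, 0.865 and 0.998. In one simulated data set the mixed-model coefficient and the mean of the two visit-specific estimates were both 0.29992.

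Under this reading a summary without visit would pool 6 × 2 = 12 values from 6 participants in a Part A active group, or 7 × 2 = 14 from 7 in Part B.

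**Step 4. CSF half-life.** SAP 3.1.4 excludes the sample at tmax and says "At least 3 data points should be used". Two post-dose CSF samples are scheduled, so at most 2 − 1 = 1 is usable against 3 required. Half-life is derivable for no participant from scheduled samples. The derivation sentence in SAP 2.3 covers serum only: "The following antibody parameters will be derived by non-compartmental analysis of the serum anti-aSyn".

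**The case against.** The strongest reply is that a programmer following the word single would enter one row per subject, so the averaging never happens. That is a fair reading. It still leaves the visit unnamed and the other visit out of the group summary and model. The code does not exclude two rows either, since its random subject term can be separated from the residual only with more than one row per subject.

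Other points:

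- **The classes are defined by number of measurements, so an endpoint measured twice belongs in the multiple class.** The definition would support this, but the SAP names these endpoints in the single class.
- **By-visit output exists.** Listings and individual graphs by visit are required, so no data are lost. They are subject-level outputs, not group summaries or treatment estimates. SAP 4.5 also promises least squares means over time, but a model without a time term cannot supply them.
- **Single is correct at the end-of-treatment analysis.** This stands: only Week 21 exists then. The protocol synopsis also plans an end-of-study analysis, when both visits exist, and SAP 4.5 is not limited to the earlier one.
- **The ratio takes Week 21 as reference, and f need not lie between 0 and 1.** Both are true. The formula is only the mean of two visit effects. It shows the size of the ambiguity, not a predicted bias.
- **The visit may be named elsewhere.** The protocol's statistical sections and part of the SAP were not in the text available, so that statement is limited to what was.
- **The study is exploratory, with no formal null hypothesis.** This limits the harm but does not remove the need to state when a primary outcome is estimated.

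**Conclusion.** The concern holds. SAP 4.5 contradicts both schedules and, for MDS-UPDRS, its own section 2.3. Followed literally, it either drops one visit from the group summary and model or merges two visits 168 days apart, and neither gives a treatment estimate at each visit.

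The size depends on the reading. With both visits entered and complete data, the estimate runs from half the Week 21 effect to all of it as the assumed ratio f goes from 0 to 1, with f common to all active arms. With one visit entered there is no averaging, only an undefined time point. The weight rests on CSF anti-aSyn titre. The point should be fixed, but it does not threaten the study: there is no formal hypothesis test, and the subject-level data remain visible by visit.

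**What to change.** 1. Move CSF antibody titres, CSF total and free aSyn, and MDS-UPDRS II/III to the multiple post-baseline class in SAP 4.5. Leave ELISpot where it is.
2. Summarise and plot these endpoints by treatment group and visit.
3. Estimate treatment contrasts separately at Week 21 and Week 45. Either fit treatment, visit, treatment-by-visit and baseline with one within-subject covariance term, or run a separate ANCOVA at each visit. Both answer the question.
4. State in advance which visit gives the main CSF anti-aSyn estimate. That choice is the sponsor's.
5. Delete CSF half-life from SAP 4.5. Review the CSF AUC request at the same time: SAP 2.3 starts the AUC at the last injection, and no CSF sample is scheduled on Day 85.

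The cost is SAP wording and a few lines of SAS. No new data or procedure is needed.
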